**Table 14 Clinical Signs and Symptoms Scoring System**

Clinical Signs and Symptoms	None	Mild	Moderate	Severe
	SCORE 0	SCORE 1	SCORE 2	SCORE 3
Dysuria				
Frequency				
Urgency				
Lower abdominal or suprapubic pain				

**Table 15 Clinical Outcome at the On-Therapy Visit**

Defining Criteria	Outcome a
Resolution of signs and symptoms of acute cystitis present at Baseline (and no new signs and symptoms), without the participant receiving other systemic antimicrobials not for the current infection before the On-therapy Visit and also without receiving an other systemic antimicrobials for the current infection prior to or at the On-therapy Visit.	Clinical resolution
Improvement in total symptom scores from Baseline, but not complete resolution, without the participant receiving other systemic antimicrobials (not for the current infection) before the On-therapy Visit and also without receiving an other systemic antimicrobials for the current infection prior to or at the On-therapy Visit.	Clinical improvement
Worsening or no change in total symptom scores from Baseline or the participant received other systemic antimicrobials for the current infection prior to or on the date of the On-therapy Visit (if the date of On-therapy Visit is missing, the end date of the analysis window will be used as the date of On-therapy visit)	Clinical worsening

 
The Baseline score is missing (unless On-therapy score is 0 and no antibiotics use (either not for current infection or for current infection) then outcome will be clinical resolution OR unless Clinical Worsening outcome criteria were met then outcome will be Clinical worsening), or
 
The On-therapy assessment is missing, (unless clinical worsening outcome criteria were met then outcome is worsening) or
 
The participant received other systemic antimicrobials not for the current infection prior to
 
	Unable to determine

Defining Criteria	Outcome a
the assessment (unless clinical worsening outcome criteria were met)	

a. A study physician or otherwise appropriately medically trained staff will determine the individual clinical signs and symptoms scores for acute cystitis (Table 14), which will then be used to programmatically determine the clinical outcome. The same scorer will be used at all assessment time points for each participant, on all occasions, whenever possible.

The text with underline is additional clarification to derive the clinical outcome in addition to the protocol table.

**Table 16 Clinical Outcome and Response at the Test-of-Cure Visit**

Defining Criteria	Outcome a	Response
Resolution of signs and symptoms of acute cystitis present at Baseline (and no new signs or symptoms), without the participant receiving other systemic antimicrobials not for the current infection before the TOC Visit and also without receiving an other systemic antimicrobials for the current infection prior to or at the TOC Visit	Clinical resolution	Clinical success
Improvement in total symptom scores from Baseline, but not complete resolution, without the participant receiving other systemic antimicrobials not for the current infection before the TOC Visit and also without receiving an other systemic antimicrobials for the current infection prior to or at the TOC Visit	Clinical improvement	Clinical failure
Worsening or no change in total symptom scores from Baseline or the participant received other systemic antimicrobials for the current infection before or on the date of the TOC Visit (if the date of TOC Visit is missing, the end date of the analysis window will be used as the date of TOC visit)	Clinical worsening	Clinical failure

 
The Baseline score is missing (unless TOC score is 0 and no antibiotics use (either not for current infection or for current infection) then outcome will be clinical resolution OR unless Clinical worsening outcome criteria were met then outcome will be Clinical worsening), or
 
The TOC assessment is missing (unless clinical worsening outcome criteria were met then outcome is worsening), or
 
The participant received other systemic antimicrobials not for the current infection prior to the assessment (unless clinical worsening criteria were met)
 
	Unable to determine	Clinical failure

TOC = Test-of-Cure

a. A study physician or otherwise appropriately medically trained staff will determine the individual clinical signs and symptoms scores for acute cystitis (Table 14), which will then be used to programmatically determine the clinical outcome. The same scorer will be used at all assessment time points for each participant, on all occasions, whenever possible.

The text with underline is additional clarification to derive the clinical outcome and response in addition to the protocol table.

**Table 17 Clinical Outcome and Response at the Follow-up Visit**

Defining Criteria	Outcome a	Response
Resolution of signs and symptoms of acute cystitis demonstrated at the TOC Visit persist at the Follow-up Visit (and no new signs and symptoms), without the participant receiving other systemic antimicrobials not for the current infection before the Follow-up Visit and also without receiving an other systemic antimicrobials for the current infection prior to or at the Follow Up Visit	Sustained clinical resolution	Clinical success
Resolution of signs and symptoms of acute cystitis present at Baseline (and no new signs or symptoms), after clinical failure at TOC, without the participant receiving other systemic antimicrobials not for the current infection before the Follow-up Visit and also without receiving an other systemic antimicrobials for the current infection prior to or at the Follow-Up Visit	Delayed clinical resolution	Clinical failure
Improvement in total symptom scores from Baseline, but not complete resolution after clinical failure at the TOC visit , without the participant receiving other systemic antimicrobials not for the current infection before the Follow-up Visit and also without receiving an other systemic antimicrobials for the current infection prior to or at the Follow-Up Visit	Clinical improvement	Clinical failure
Worsening or no change in total symptom scores at Follow-up compared to Baseline after clinical failure at TOC, or the participant received other systemic antimicrobials for the current infection before or on the date of the Follow-up Visit (if the date of Follow-Up Visit is missing, the end date of the analysis window will be used as the date of Follow-Up visit)	Clinical worsening	Clinical failure
Signs and symptoms of acute cystitis reoccur at the Follow-up Visit (can be improved (but not resolution) OR worsening or no change from baseline i.e., (1) change from baseline at Follow-Up visit < 0 AND score is not 0 at Follow-Up Visit (2) change from baseline at the Follow-Up visit >= 0) after clinical success at TOC without the participant receiving an other systemic antimicrobials for the current infection prior to or at the Follow-Up visit	Clinical recurrence	Clinical failure
1) The Baseline score is missing (unless Follow-Up score is 0 and no antibiotics use (either not for current infection or for current infection) then outcome will be clinical resolution (delayed or sustained as appropriate) OR unless Clinical worsening outcome criteria were met then outcome will be clinical worsening) , or 2) The Follow-up assessment is missing (unless clinical worsening outcome criteria were met then outcome is clinical worsening) , or	Unable to determine	Clinical failure

Defining Criteria	Outcome a	Response
3) The participant received other systemic antimicrobials not for the current infection prior to the assessment (unless the clinical worsening or recurrence outcome criteria were met)		

TOC = Test-of-Cure

a. A study physician or otherwise appropriately medically trained staff will determine the individual clinical signs and symptoms scores for acute cystitis (Table 14), which will then be used to programmatically determine the clinical outcome. The same scorer will be used at all assessment time points for each participant, on all occasions, whenever possible.

The text with underline is additional clarification to derive the clinical outcome in addition to the protocol table.

#### 6.2.1.3. Fold change on susceptibility

Fold change will be used to describe how much the MIC for gepotidacin and nitrofurantoin changes between baseline and subsequent visits for the same bacterial species from the same participant based on the broth microdilution results. Fold change will be calculated (in doubling dilutions) as the ratio of the MIC at the subsequent visit to the MIC at Baseline Visit. However, ratio of 1 will be reported as 0-fold ratio. Ratio less than 1 will be reported in reciprocal with negative sign (e.g. ratio of 0.5 will be reported as -2 fold). Examples:

Baseline MIC (mcg/mL)	Post-baseline MIC (mcg/mL)	Fold-change
1	1	0-fold
1	2	2-fold
1	4	4-fold
1	8	8-fold
1	16	16-fold
1	0.5	- 2-fold
1	0.25	- 4-fold
1	>32	>/=64-fold
1	>/=32	>/=32-fold
1	<0.125	>/= - 16-fold
1	</=0.125	>/= - 8-fold

#### 6.2.1.4. MIC50 and MIC90

MIC50 and MIC90 are defined as the 50th and 90th percentile of the MIC values. They will only be reported if the number of uropathogens is larger or equal to 10. MICxx is defined as follows.

$$MIC_{xx} = \min_j \{x_j; \hat{F}(x_j) \geq xx\% \}$$

, where  $x_j$  is MIC value and  $\hat{F}(\cdot)$  is empirical cumulative distribution.

For an even number of samples, the MIC50 is the next one above the median. Similar algorithm applied to MIC90.

### 6.2.1.5. Investigator-Assessed Clinical Response

Definitions	Clinical Response
Sufficient resolution of acute cystitis signs and symptoms such that no additional systemic antimicrobial therapy is required for the current infection	Clinical Success
Participant met any one of the criteria below: 
 
• No apparent response to treatment (persistence or progression of any pretreatment clinical signs and symptoms)
 
• Use of additional systemic antibiotic(s) for the current infection
 
• Death related to acute cystitis prior to the visit
 
	Clinical Failure
Determination of clinical response could not be made at the visit for any of the following reasons: 
 
• Participant was lost to follow-up and/or the clinical assessment was not undertaken
 
• Use of confounding systemic antibiotic(s) for another infection
 
• Death prior to the visit where acute cystitis was clearly noncontributory
 
	Indeterminate

Missing data will be handled based on the table below.

Scenario	Date of data at EW (early withdrawal) Visit	Response at EW visit	Reason for response at EW visit	Start date of Antibiotics use for uUTI	Derivation of data
Missing at TOC	Date < 17 days + baseline	Clinical Failure OR Indeterminate	“Death” is contained	NA	Same as data at EW visit
Missing at TOC	Any date	Clinical Failure	“Use of additional systemic antibiotic(s) for the current infection”	Baseline <= date <= 17 days + baseline	Same as data at EW visit
Missing at Follow-Up	Date < 31 days + baseline	Clinical Failure OR Indeterminate	“Death” is contained	NA	Same as data at EW visit
Missing at Follow-Up	Any date	Clinical Failure	“Use of additional systemic antibiotic(s) for the current infection”	Baseline <= date <= 31 days + baseline	Same as data at EW visit
Any other missing other than the above				Response: Indeterminate/missing Reason: Participant was lost to follow-up and/or the clinical assessment was not undertaken/missing	

CCI

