- For the primary efficacy endpoint of therapeutic response (combined per-participant microbiological and clinical response), therapeutic success refers to participants who have been deemed both a microbiological success (reduction of all qualifying bacterial uropathogens [e.g., $\geq 10^5$ CFU/mL; defined in [10.8](#)] recovered at Baseline to $< 10^3$ CFU/mL as observed on quantitative urine culture without the participant receiving other systemic antimicrobials) and a clinical success (resolution of signs and symptoms of acute cystitis present at Baseline [and no new signs and symptoms] without the participant receiving other systemic antimicrobials) at the TOC Visit in the Microbiological Intent-to-Treat Nitrofurantoin-Susceptible (micro ITT NTF-S) Population, regardless of treatment discontinuation.
- PK samples will be collected in all participants for analysis at the Baseline (postdose) and the On-therapy Visits (predose and postdose).
- Participants may return to the study site at any time due to AEs or if they are experiencing new or continuing signs and symptoms of acute uncomplicated cystitis.

Participants will be assessed and treated per the investigator's judgement. If a participant is switched to a different antimicrobial before or during the TOC Visit, all TOC procedures should be completed before the other antimicrobial is started.

- Participants with a concomitant fungal infection can only be treated with topical antifungals per local standard of care.
- Participants will return to the study site on Day 28 (± 3) for a Follow-up Visit. Participants experiencing signs and symptoms suggestive of infection recurrence or relapse will be assessed and treated per the investigator's judgement.
- The study duration is approximately 28 days with 4 planned study visits (see Section 8 for study visit details):
 - Baseline (Day 1) Visit
 - On-therapy (Day 2 to 4) Visit
 - TOC (Day 10 to 13) Visit
 - Follow-up (Day 28 ± 3) Visit

A study design schematic is depicted in [Figure 1](#). The Schedule of Activities (SoA) is provided in Section [1.3](#).

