#### 4.3.7.2. Main analytical approach

This analysis is based on ITT Population. Below are the categories of response and response.

Definition	Clinical Response
Sufficient resolution of acute cystitis signs and symptoms such that no additional systemic antimicrobial therapy is required for the current infection	Clinical Success
Participant met any one of the criteria below: 
 
• No apparent response to treatment (persistence or progression of any pretreatment clinical signs and symptoms)
 
• Use of additional systemic antibiotic(s) for the current infection
 
• Death related to acute cystitis prior to the visit
 
	Clinical Failure
Determination of clinical response could not be made at the visit for any of the following reasons: 
 
• Participant was lost to follow-up and/or the clinical assessment was not undertaken
 
• Use of confounding systemic antibiotic(s) for another infection
 
• Death prior to the visit where acute cystitis was clearly noncontributory
 
	Indeterminate

The missing data at TOC visit including outside the analysis window will be handled as shown in Section [6.2.1.5](#).

The number and proportion of participants with investigator assessed clinical response of success, failure and indeterminate/missing at the TOC Visit by treatment group based on ITT Population. Reasons for an assessment of failure and indeterminate responses will also be summarized.

The 95% Exact Clopper Pearson CI for the proportion of participants with success will be presented as a binomial proportion for each treatment group.

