## 6.2.7. Assessment Window

Unscheduled and withdrawal visit data will be slotted into a target visit based on visit window defined in the table below. If there are multiple assessments within the same window, the closest one to the target day will be taken in the slotting. If multiple records are equally close to the target day, then the later record will be utilized. For post-baseline records collected outside the analysis visit window, a blank analysis visit label will be assigned.

Analysis Set / Domain	Parameter (if applicable)	Target	Analysis Window		Analysis Timepoint
			Beginning Timepoint	Ending Timepoint	
All	All	Day 3	Day 2	Day 5	On-therapy
All	All	Day 12	Day 9	Day 16	Test-of-Cure
All	All	Day 28	Day 21	Day 31	Follow-up

The procedure of the analysis visit assignment is as follows.

1. Calculate the analysis days for planned visit, unscheduled visit, and early withdrawal visit with non-missing outcome if applicable. The calculation of the analysis days is provided in Section 6.2.6.
2. Slot the visits to each of analysis timepoint according to the above table.
  - a. If there are multiple assessments within the same windows, the closest one to the target day will be taken in the slotting.
  - b. If multiple records are equally close to the target day, then the later record will be utilized using the sequence number in SDTM dataset.
  - c. For post-baseline records collected outside the analysis visit window, a blank analysis visit label will be assigned. Such assessments will not be included in any of the by visit summaries. Descriptive summaries that are shown for “any assessment post baseline” e.g. maximum/minimum/ worst case post baseline, will use all assessments irrespective of whether they fall in an analysis visit window.

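### For a missing Test-of-Cure investigator response, SAP 6.2.1.5 counts antibiotic rescue as failure only with an early-withdrawal record, contrary to the composite strategy and Table 16

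*SAP*

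**What the plan says.** SAP 4.3.7.1 defines the endpoint. The summary measure is the proportions with success, failure and indeterminate/missing. Study treatment discontinuation is handled by treatment policy, and systemic antimicrobials on or before the visit by a composite strategy. The definitions in 4.3.7.2 and 6.2.1.5 list additional systemic antibiotics for the current infection as a Clinical Failure criterion.

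On missing data, 4.3.7.2 says: "The missing data at TOC visit including outside the analysis window will be handled as shown in Section" 6.2.1.5. At TOC, the table there carries a result over in two situations, both requiring an early-withdrawal visit:

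- The reason contains death, and the visit is dated before baseline + 17 days.
- The response is Clinical Failure for additional antibiotics, and the antibiotic start satisfies "Baseline <= date <= 17 days + baseline".

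The last row covers "Any other missing other than the above". It sets the response to Indeterminate/missing and the reason to: "Reason: Participant was lost to follow-up and/or the clinical assessment was not undertaken/missing".

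Four other provisions decide who reaches that last row.

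- SAP 6.2.7: the TOC window is Day 9 to Day 16, and unscheduled and withdrawal visits inside it are slotted to TOC. Otherwise: "For post-baseline records collected outside the analysis visit window, a blank analysis visit label will be assigned".
- Protocol 4.1, for a woman switched before or during TOC: "all TOC procedures should be completed before the other antimicrobial is started".
- Protocol 7.1: women who discontinue study treatment are not considered withdrawn and should attend their remaining visits.
- SAP Table 16, for the programmed clinical response: antibiotics for the current infection on or before the TOC date give clinical worsening and failure, even when the TOC assessment is missing. It adds: "if the date of TOC Visit is missing, the end date of the analysis window will be used as the date of TOC visit".

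**The concern.** The rescue row depends on a type of visit that a rescued woman is not expected to have. She has stopped study treatment but has not left the study, so no early-withdrawal record arises. If she is switched early, her TOC procedures are done early and fall outside the TOC window. Unless she is assessed again on Day 9 to 16, the last row applies.

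Three things follow. The composite strategy is not carried out for these women. The two clinical endpoints at TOC disagree for the same woman with no reason given. The reasons table can report an assessment as not undertaken or missing when one was made before the switch.

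At stake are the failure and indeterminate/missing proportions, which are part of the stated summary measure, and the tabulated reasons.

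**Working it through.** **Rule check.** I followed seven constructed paths through SAP 6.2.7, the 6.2.1.5 table and Table 16. In each, an antibiotic for the current infection is started. They show how the rules act, not how often each path occurs.

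| Path | Investigator response, 6.2.1.5 | Programmed response, Table 16 |
|---|---|---|
| Antibiotic Day 6; early-withdrawal visit Day 6, Failure, antibiotic reason | Failure | Worsening, failure |
| Antibiotic Day 10; early-withdrawal visit Day 10, Failure | Failure (slotted to TOC) | Worsening, failure |
| Antibiotic Day 7; stays in study, TOC Day 11, Failure | Failure (in window) | Worsening, failure |
| TOC procedures Day 8, Failure, then switched; not seen again on Day 9 to 16 | Indeterminate/missing | Worsening, failure |
| TOC procedures Day 4, Failure, then switched; not seen again on Day 9 to 16 | Indeterminate/missing | Worsening, failure |
| Antibiotic Day 5 in the medication record; no early-withdrawal visit, TOC missed | Indeterminate/missing | Worsening, failure |
| Antibiotic Day 6; early-withdrawal visit Day 6, Failure, reason recorded as no response | Indeterminate/missing | Worsening, failure |

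The first three paths agree and the last four do not. In the Day 4 path, the record slots to the On-therapy window (Day 2 to 5), a visit at which the Schedule of Activities has no investigator response.

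**Cut-offs.** SAP 6.2.6 gives study day = date − reference date + 1. I take baseline in the table to be the reference date.

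- TOC antibiotic row: date ≤ baseline + 17, so up to Study Day 17 + 1 = 18.
- TOC death row: date < baseline + 17, so up to baseline + 16 = Study Day 17.
- TOC window end: Day 16 = baseline + 15.
- Follow-up antibiotic row: date ≤ baseline + 31, so up to Study Day 32.
- Follow-up death row: date < baseline + 31, so up to Study Day 31.
- Follow-up window end: Day 31 = baseline + 30.

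Only the Follow-up death row matches its window. If 17 was meant as a study day, it still differs from 16.

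**Size per woman.** The documents give no figure for this rule. The planned sample is 300 randomised 3:1 (SAP 5.1.3); as a check on those inputs, 300 × 0.36 = 108, the stated evaluable target. The SAP analyses this endpoint in the ITT set.

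- Gepotidacin: 300 × 3/4 = 225; 1/225 = 0.44 percentage points.
- Nitrofurantoin: 300 × 1/4 = 75; 1/75 = 1.33 points.

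The SAP's ITT set leaves out one site because of a GCP violation, so at 300 randomised the actual denominators would be somewhat smaller and the step per woman somewhat larger. As an assumption only, one to five such women on gepotidacin would move 0.44 to 2.2 points (5/225).

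**The case against.** The strongest reply is that the rule reaches few women. A rescued woman with an early-withdrawal failure for antibiotic use stays a failure whatever the date of that visit. Early-withdrawal and unscheduled visits on Day 9 to 16 are slotted to TOC and keep their value. Women who stop treatment are meant to return, and an investigator who sees them in the window has antibiotic use as a listed failure criterion. All of this stands. The gap is confined to rescued women with neither an in-window assessment nor a qualifying early-withdrawal record.

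It can also be said that indeterminate women are still non-successes, so the composite strategy is met in substance. That does not answer the point. The summary measure has three categories, and the SAP's own definition places antibiotics for the current infection under failure.

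A reader might infer more than the documents support, in four ways.

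- *That every early failure should be carried to TOC.* An early-withdrawal failure on Day 6 to 8 for "No apparent response to treatment (persistence or progression of any pretreatment clinical signs and symptoms", without rescue, also becomes indeterminate. But a poor response just after a 5-day course does not settle the response at Day 10 to 13. Table 16 likewise gives an outcome of unable to determine when TOC is missing and no antibiotic was taken, although its binary response is failure. Carrying such a failure forward is a debatable choice, not a correction.
- *That the assigned reason is always false.* The wording includes an assessment not undertaken or missing, which is accurate for a woman who simply missed TOC. It misdescribes only a woman whose assessment was made outside the window.
- *That the cut-offs add to the loss of failures.* They act the other way, because a later limit keeps more antibiotic failures. They are an inconsistency in their own right.
- *That the failure proportion is understated by several points.* No document gives the rate needed to say so.

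**Conclusion.** The point holds in a narrow form. For women who start a systemic antibiotic for the current infection and have neither an in-window TOC investigator assessment nor an early-withdrawal failure recorded for that reason, SAP 6.2.1.5 does not carry out the composite strategy in 4.3.7.1 and conflicts with Table 16. The cut-off days do not match the 6.2.7 windows, except in the Follow-up death row.

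The effect is limited to the split between failure and indeterminate/missing and to the reasons table: 0.44 points per woman on gepotidacin and 1.33 on nitrofurantoin, at planned size. The total depends on how many rescued women are not assessed on Day 9 to 16, which cannot be derived from the documents. The success proportion and its Clopper-Pearson interval do not change. Nor does the primary therapeutic response, which is programmed from symptom scores and cultures. The endpoint is a descriptive secondary summary, so no test is affected. The correction is still worth making, because the plan states an estimand that its derivation does not deliver.

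**What to change.** Amend the missing-data table in SAP 6.2.1.5:

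1. When the in-window TOC response is missing, assign Clinical Failure with the existing antibiotic-use reason if the medication record shows a systemic antibiotic for the current infection started from Day 1 to the end of the TOC window. Require no early-withdrawal record, as in Table 16. Apply the same rule at Follow-up with its own window.
2. Replace the baseline-plus-days limits with the 6.2.7 window ends, Study Day 16 for TOC and Study Day 31 for Follow-up, using the same inequality in the death and antibiotic rows.
3. Where an investigator assessment was made outside the window and is not carried to TOC, report that as the reason in place of the lost-to-follow-up text.

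The data needed are already collected: protocol 6.8 requires the reason and dates for every concomitant medication. The cost is a short SAP amendment and a small programming change. The reported failure proportion may rise slightly, with an equal fall in indeterminate/missing.
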